### 8.5 Study Drug Accountability

An accurate and current accounting of the dispensing and return of study drug for each subject will be maintained on an ongoing basis by a member of the study site staff based on the records maintained by the pharmacists at the pharmacy site. The number of study drugs transferred to the pharmacy site, dispensed and returned by the subject will be recorded on the Investigational Drug Accountability Log. The study PI will verify these documents throughout the course of the study.

## 8.6 Measures of Treatment Compliance

Participant patients will be contacted on Day 2 to complete the Day 2 Survey, which is detailed below in section 10.2. As part of this survey, patients will be asked if and when they took the Mifeprex®. If they have not yet taken the Mifeprex®, they will be asked when they plan to take it, and they will be contacted after that date to complete the Day 2 Survey. If they obtained the Mifeprex® in the study pharmacy but decided not to take it, they will be asked whether they returned it to the study clinic or pharmacy as instructed.

# 9 STUDY PROCEDURES AND GUIDELINES

The UCSF study team will train sites on standardized recruitment and consent procedures and have regular communication with study clinics and pharmacies to provide technical assistance and check on progress of the study. Data collection tools and procedures will be pilot tested before implementation. Data will also be monitored periodically to ensure that data collection, coding, and management procedures are being conducted according to protocol and ethical guidelines.

Prior to conducting any study-related activities, written informed consent must be signed and dated by the subject. If appropriate, assent must also be obtained prior to conducting any study-related activities.

## 9.1 Clinical Assessments

All clinical assessments will be documented in the medical record, and this information will be abstracted from the medical record for analysis.

### 9.1.1 Concomitant Medications

Concomitant medications such as antibiotics and analgesics will be documented at each clinical visit, and this information will be abstracted from the medical record.

### 9.1.2 Demographics

Demographic information (age, parity, race, and ethnicity) will be recorded as part of the initial visit and will be abstracted from the medical record (see list of variables to be abstracted in Appendix G). The site PI will supervise the data abstraction and replace the name with the Study ID prior to transferring the data to the UCSF research team. Demographic information will also be collected on the Day 2 Survey (see section 10.2).

### 9.1.3 Medical History

At the initial visit, the following will be recorded in the medical record: date of service, gestational age by ultrasound and date of ultrasound, past medical history, current medications, blood pressure, weight, height, and medications prescribed or dispensed (Mifeprex® 200 mg, misoprostol 800 mcg, antibiotics, analgesics, other). At any follow-up visits, unusual symptoms such as heavy bleeding, pain or fever will be recorded, as well as any treatment given. Women will also be asked if they sought care elsewhere since the prior visit, and if so, what treatment, if any, they were given.

#### 9.1.4 Physical Examination

Blood pressure, weight, height, and ultrasound data will be collected at the initial visit. A targeted physical examination will be performed at the clinic site according to their current practice.

#### 9.1.5 Vital Signs

Vital signs will be recorded at each clinical encounter.

#### 9.1.6 Ultrasound

Ultrasound may be performed at the initial visit to determine gestational age of the pregnancy (if it is not performed at the clinic site, the date and result of an outside ultrasound must be documented). Ultrasound may be performed at a follow-up visit to determine whether the abortion is complete or incomplete or if there is an ongoing pregnancy.

#### 9.1.7 Other Clinical Procedures

Patients may undergo uterine aspiration in case of heavy bleeding, incomplete abortion or ongoing pregnancy. This procedure will be detailed in the medical record.

#### 9.1.8 Adverse Events

We will track adverse events (AEs) as described in section 11.

### 9.2 Clinical Laboratory Measurements

#### 9.2.1 Pregnancy Test

Women will be presenting for pregnancy termination, so pregnancy will be confirmed as part of the visit prior to recruitment, consent, and enrollment.

#### 9.2.2 Hemoglobin

Most patients will have hemoglobin measured in the clinic, and this result with the date of the test will be abstracted from the medical record.

#### 9.2.3 Serum human chorionic gonadotropin (hCG)

Some patients will have serum hCG measured on the day of Mifeprex® administration and again approximately 8 days later to assess for completion of the abortion. These results with the date of the tests will be abstracted from the medical record.

## 10 ACTIVITIES BY DAY –PATIENTS

### 10.1 Day 1

This is the day the patient participant is enrolled in the study. Patients choosing medication abortion will undergo standard assessment, including an ultrasound for gestational age assessment, if it has not yet been performed, and counseling. **Once women have signed the Danco Patient Agreement and any**

other specific consent forms for the site, they will be assessed for eligibility to participate in this study and undergo the informed consent process for this study on paper or iPad (Appendix B). Contact information and contact preferences will also be obtained (on an iPad; Appendix C). Study participants will be given a prescription for Mifeprex® 200 mg, misoprostol 800 mcg, and any other necessary medications (or the prescriptions will be electronically transmitted), as well as information about when and how to take the medications. At the pharmacy, the pharmacist will review the prescription and dispense Mifeprex® 200 mg (1 tablet) and misoprostol 200 mcg (4 tablets) as ordered. The lot number of all medications will be recorded in the standard fashion, and the dispensing pharmacist will also record the dispensing of the study medication in the Investigational Drug Accountability.

## 10.2 Day 2 Survey

On the following day, patient participants will be sent by email or text message, depending on their preference, a link to an online survey about their experience obtaining the medications, as well as to collect sociodemographic information (see Day 2 survey, Appendix H). Participants will be asked to complete the survey after going to the pharmacy to obtain Mifeprex®. If a participant prefers, or if she does not respond to the email link, she may be contacted by telephone to complete the survey over the phone or sent reminders by text message. The survey will focus on her experience in the pharmacy, including how she was treated and the information she received, as well as her experience taking the Mifeprex®. If the participant went to a pharmacy that was not her usual pharmacy, we will ask about her perspective on having to go to a different pharmacy. We will also collect information about if and when the Mifeprex® and misoprostol and if the Mifeprex® might have been diverted to another person. If they do not respond to the survey by Day 4, participants will be contacted up to three times (each day for three subsequent days to complete the survey). If a participant has decided not to proceed with medication abortion (because she has decided to have a surgical abortion or continue the pregnancy or because she needs more time to decide), she will be encouraged to complete the Day 2 survey, where this information will be captured. If a woman obtained the Mifeprex® and/or misoprostol and has decided not to take the medication(s), she will be asked to return them to the pharmacy or the clinic.

## 10.3 Clinical follow-up

Women undergoing medication abortion generally undergo clinical follow-up to ensure that the abortion is complete. This may include a follow-up visit or a phone call from clinic staff approximately 7-14 days after the initial visit. In some cases, serum hCG may be measured on the day of Mifeprex® administration and again approximately 8 days later to assess for completion of the abortion. No study-related activities will be performed as part of this clinical follow-up. Management of incomplete abortion without hemorrhage will be done according to the standard practice at the site, and may include expectant management, an additional dose of misoprostol, or vacuum aspiration. Participants with ongoing pregnancy will be managed according to the standard practice at the site, and may include an additional dose of misoprostol, repeating Mifeprex® and misoprostol or vacuum aspiration. No study activities will take place at this visit, although clinical information recorded at this visit will be later abstracted from the patient's record (see section 9.1).

## 10.4 Day 14 Survey

On Day 14 after the initial clinic visit, patient participants will be sent by email or text message, depending on their preference, a link to an online survey about their overall satisfaction with the medication abortion process and to obtain information about whether the abortion has been completed (see Day 14 Survey, Appendix I). If a participant prefers, or if she does not respond to the email link, she may be contacted by telephone to complete the survey over the phone or sent reminders by text message. If the participant is unsure if the abortion is complete, we will instruct

her to contact the clinic and ask for permission to contact her one week later. If they do not respond to the survey, participants will be contacted up to three times.

## 10.5 Data Abstraction

As noted above in section 9, de-identified data about the clinical visits of participants consenting for the study will be abstracted from the electronic medical record system of the participating sites. This includes clinical information including demographics (age, parity, race, ethnicity), initial visit information (date of service, gestational age, past medical history, medications, laboratory values), and follow-up visit information (date of service, treatment given, symptoms, outcome of abortion, adverse events, and other follow-up care). The site PI will perform a chart review for each participant 6 weeks after enrollment. De-identified data will be entered into a Qualtrics or REDCap electronic form (see Appendix G for the variables that will be abstracted). As noted above, the site PI will supervise the data abstraction and replace the participant name with the Study ID prior to transferring the data to the UCSF research team.

# 11 EVALUATIONS – PHARMACISTS

## 11.1 Baseline Survey/Interview

Each of the pharmacists at the study sites will be invited to participate in a survey and interview prior to the initiation of Mifeprex® dispensing. This survey and interview will focus on baseline knowledge of medication abortion, comfort with dispensing Mifeprex®, anticipated challenges of dispensing Mifeprex®, and whether the respondent plans to refuse to participate in Mifeprex® dispensing (and why). The survey may be completed on paper or online (see Appendix J), and the pharmacists will provide verbal or click-through consent to the survey and interview (Appendix E). Only pharmacists who indicate on the survey that they would be willing to participate in a follow-up interview will be contacted for an interview. The interview, which may be performed in person or over the phone and will be recorded if participants agree, will allow for collection of qualitative data about their perceptions of implementing the new service (Appendix K). The consent which was administered prior to the survey will be reviewed briefly prior to the interview, and consent to record the interview will be confirmed and documented.

## 11.2 Monthly Assessments

Each month after initiating the study, research staff at UCSF will contact the supervising pharmacist at each pharmacy site to assess the number of pharmacists working at the site, whether any pharmacist has started to dispense Mifeprex®, and whether any pharmacist has stopped dispensing Mifeprex®.

## 11.3 End-line Survey

Each of the pharmacists at the study sites will be invited to participate in a survey and interview at the end of the study. This survey and interview will focus on knowledge of medication abortion, comfort with dispensing Mifeprex®, experienced challenges of dispensing Mifeprex®, and whether the respondent refused to participate in Mifeprex® dispensing at any point (and why). Respondents who report having refused to dispense Mifeprex® will be asked about whether patients were referred to another pharmacist who was able to dispense, and if so, how that process worked. The survey may be completed on paper or online (see Appendix L), and the pharmacists will provide verbal or click-

through consent to the survey and interview (Appendix E). Only pharmacists who indicate on the survey that they would be willing to participate in a follow-up interview will be contacted for an interview. The interview which may be performed in person or over the phone and will be recorded if participants agree, will allow for collection of qualitative data about their perceptions of implementing the new service (Appendix M). The consent which was administered prior to the survey will be reviewed briefly prior to the interview, and consent to record the interview will be confirmed and documented.

An AE is any untoward medical occurrence in a clinical investigation of a patient administered a pharmaceutical product and that does not necessarily have a causal relationship with the treatment. An AE is therefore any unfavorable and unintended sign (including an abnormal laboratory finding), symptom or disease temporally associated with the administration of an investigational product, whether or not related to that investigational product. An unexpected AE is one of a type not identified in nature, severity, or frequency in the current Mifeprex® label or of greater severity or frequency than expected based on the information in the label.

The following definitions apply to adverse events occurring in clinical studies involving drugs:

- An AE is any health-related reaction, effect, toxicity or abnormal laboratory result that a participant experiences during the course of the study, irrespective of relationship to study product use.

In this study, the following routine study measurements will not be considered AEs because they are anticipated participant outcomes:

- Abortion
- Symptoms associated with medication abortion (pain, vaginal bleeding, fever, chills, nausea, vomiting, headache, weakness, dizziness and diarrhea), unless they are so severe as to meet the criteria for a SAE (see section 12.2 below)

12.1.1 AE Severity

The National Cancer Institute’s Common Terminology Criteria for Adverse Events (CTCAE) Version 3.0 should be used to assess and grade AE severity, including laboratory abnormalities judged to be clinically significant. Table 1 below should be used to grade severity. It should be pointed out that the term “severe” is a measure of intensity and that a severe AE is not necessarily serious.

**Table 1. AE Severity Grading**

Severity (Toxicity Grade)	Description
Mild (1)	Transient or mild discomfort; no limitation in activity; no medical intervention or therapy required. The subject may be aware of the sign or symptom but tolerates it reasonably well.
Moderate (2)	Mild to moderate limitation in activity, no or minimal medical intervention/therapy required.
Severe (3)	Marked limitation in activity, medical intervention/therapy required, hospitalizations possible.
Life-threatening (4)	The subject is at risk of death due to the adverse experience as it occurred. This does not refer to an experience that hypothetically might have caused death if it were more severe.

### 12.1.2 AE Relationship to Study Drug

The relationship of an AE to the study drug should be assessed using the following the guidelines in Table 2.

**Table 2. AE Relationship to Study Drug**

Relationship to Drug	Comment
Definitely	Previously known toxicity of agent; or an event that follows a reasonable temporal sequence from administration of the drug; that follows a known or expected response pattern to the suspected drug; and that is not explained by any other reasonable hypothesis.
Probably	An event that follows a reasonable temporal sequence from administration of the drug; that follows a known or expected response pattern to the suspected drug; and that is unlikely to be explained by the known characteristics of the subject's clinical state or by other interventions.
Possibly	An event that follows a reasonable temporal sequence from administration of the drug; that follows a known or expected response pattern to that suspected drug; but that could readily have been produced by a number of other factors.
Unrelated	An event that can be determined with certainty to have no relationship to the study drug.

### 12.2 Serious Adverse Events (SAE)

A serious adverse event (SAE) is defined as any untoward medical occurrence that:

- Is life threatening or results in death.
- Requires in-patient hospitalization or prolongs existing hospitalization.
- Results in persistent or significant disability/incapacity.
- Is a congenital abnormality/birth defect (in the offspring of a participant).
- Jeopardizes participant and required medical/surgical intervention to prevent serious outcome, *or*
- Any other event that the investigator considers serious.

#### 12.2.1 Serious Adverse Event Reporting

Study sites will document all SAEs that occur (whether or not related to study drug) per [UCSF IRB Guidelines](#). The collection period for all SAEs will begin after informed consent is obtained and end six weeks after the visit where Mifeprex® is prescribed.

In accordance with the standard operating procedures and policies of the local IRB/the site PI will report SAEs to the IRB.

## 13 DISCONTINUATION AND REPLACEMENT OF SUBJECTS

### 13.1 Early Discontinuation of Study Drug

Because participants will only take a single dose of Mifeprex®, there will be no opportunity to discontinue treatment. If a patient vomits within 30 minutes after taking Mifeprex®, she will be instructed to return to the clinic site for further evaluation and management.

### 13.2 Withdrawal of Subjects from the Study

A subject may be withdrawn from the study at any time if the subject, the site PI, or the PI feels that it is not in the subject's best interest to continue.

All subjects are free to withdraw from participation at any time, for any reason, specified or unspecified, and without prejudice.

Reasonable attempts will be made by the site PI to provide a reason for subject withdrawals. The reason for the subject's withdrawal from the study will be specified in the subject's data collection documents.

### 13.3 Replacement of Subjects

If any subject withdraws or does not complete the study as planned, they will be replaced with an additional participant.

## 14 PROTOCOL VIOLATIONS

A protocol violation occurs when the subject, investigator, or clinic or pharmacy staff fails to adhere to significant protocol requirements affecting the inclusion, exclusion, subject safety and primary endpoint criteria. Potential protocol violations for this study include, but are not limited to, the following:

- Failure to meet inclusion/exclusion criteria
- Failure to comply with Good Clinical Practice (GCP) guidelines. The PI will determine if a protocol violation will result in withdrawal of a subject.

When a protocol violation occurs, it will be discussed with the site PI and a Protocol Violation Form detailing the violation will be generated. This form will be signed by the PI and the site PI. A copy of the form will be filed in the site's regulatory binder and in the PI's files.

## 15 DATA SAFETY MONITORING

Safety oversight will be under the direction of the PI. Because Mifeprex® is already approved, and there is a great deal of safety data on its use for this approved indication, we think it is reasonable for safety monitoring to occur through the standard review of S/AE reports (see section 12).

As part of routine instruction in the FDA's Mifeprex® Medication Guide provided to women undergoing medication abortion, participants will be instructed to return to the study site or a nearby facility offering emergency care in the case of heavy bleeding (more than 2 full-size pads soaked per hour for 2 hours), abdominal pain or "feeling sick", fever of 100.4 degrees or higher persisting more than 4 hours or for any signs of complications.

## 16 STATISTICAL METHODS AND CONSIDERATIONS

Prior to the analysis of the final study data, a detailed Statistical Analysis Plan (SAP) will be written describing all analyses that will be performed. The SAP will contain any modifications to the analysis plan described below.

### 16.1 Data Sets Analyzed

All eligible patients who receive the dose of the study drug will be included in the analysis. All eligible pharmacists who complete at least one survey or interview will be included in the pharmacist analysis.

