Pharmacist participants will include any pharmacist working at one of the study pharmacy sites during the study who is willing to participate in the study. All pharmacists employed at the pharmacy sites will have a choice about participating in the research in terms of dispensing mifepristone and receiving the training, and in terms of completing the interviews/surveys. We have confirmed that there is at least one pharmacist at the site who is willing to dispense mifepristone. The baseline survey asks pharmacists if they plan to dispense mifepristone during the study. This will alert the research team if any pharmacists at a site say they do not plan to dispense, however, the research team will keep this information confidential. All pharmacists will be invited to the initial study training which will take place after baseline data collection. Pharmacists will be told that in order to dispense mifepristone they must receive the study training. (Remote training can be provided for interested pharmacists who were not able to attend the in-person session.) By knowing the number of pharmacists who have been trained and the total number of pharmacists that work at each site, we will have an idea of how many pharmacists will not be participating in the study dispensing. All trainings for pharmacists will include schedule mapping among participants to ensure that trained pharmacists are available to dispense to study participants during business hours. At the end of the training, pharmacists will be asked again whether they plan to dispense mifepristone during the study, as a check to assess whether sites may have any scheduling issues. We may also follow up with a lead pharmacist or pharmacy manager to confirm availability of trained pharmacists and work out a system for ensuring mifepristone is available to patients. We will conduct periodic check ins with the pharmacy manager/lead pharmacist since pharmacy staffing throughout the study period may fluctuate. Any new pharmacists will be reached with the study consent and baseline survey and the research team will provide training to interested pharmacists (remote training as needed). Our periodic check-ins can also assess how smoothly the study is running at the pharmacy and whether any pharmacists

have expressed concerns about or hesitation to dispense mifepristone.

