## 8.2 Method of Recruitment for Pharmacists

All pharmacists at the study pharmacies will be eligible. Pharmacists will be invited to participate in the survey/interview prior to initiating the study and at the end of the study by email/flyer and through face-to-face visits by study staff (see draft email in Appendix D). We will obtain the email addresses of pharmacists when we visit the pharmacy to introduce and launch the study. Pharmacists will voluntarily provide their email addresses. All pharmacists employed by the pharmacy sites will have a choice about participating in the research in terms of dispensing mifepristone and receiving the training, and in terms of completing the interviews/surveys. In the baseline survey, they will be asked whether they plan to dispense mifepristone when the pharmacy begins offering it. All pharmacists will be invited to a training and study launch to take place at their pharmacy. The training/study launch will involve the UCSF PI and/or site PI and research team presenting an overview of medication abortion and the aims and procedures of the study. They will also receive a binder of resource materials for the study, which they can refer to for further information throughout the study period.

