A pharmacist can participate in up to two surveys (baseline and endline) and two interviews (baseline and endline) but may decline to participate in any. We expect that there may be staffing changes from the beginning of the study to the end, so some may participate only in baseline data collection or only endline data collection. The survey includes a question asking if pharmacists would be willing to participate in an interview. Only those who respond "yes" will be contacted for interviews. The informed consent (Appendix E) will be used at beginning of the study to describe all of the study activities, including the baseline survey and interview, the endline survey and interview, and the training and dispensing. The consent will be used again at the end of the study before the endline survey and interview. The consent document for the pharmacists will not record the pharmacists' names or the names of the pharmacy, however we will program the surveys so that each pharmacy has a different link. This is how we will know which pharmacy respondents are from. It will also alert us if someone from a certain pharmacy does NOT consent to the training (identifying possible scheduling needs at this site). While not linked with survey responses, we do also collect email in the pharmacy survey in order to send a gift card. We have added a question asking if it is okay to contact them with details about the study training.

The consent includes language asking if pharmacists consent to audio recording of the interview. Since the interview may not happen immediately after the consent, we will confirm and document that pharmacists consent to audio recording before beginning the interview. Pharmacists can still participate in the study even if they decline the audio recording. Interviews will be scheduled at a convenient time when they do not interfere with the pharmacists' work.

The consent will also include description of the training and ask whether the pharmacist consents to the training.

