### 16.3 Analysis of Primary Endpoint

Feasibility of the pharmacy dispensing model will be assessed in quantitative descriptive analyses of satisfaction variables from the pharmacists' end line survey (overall satisfaction, perceived benefits/challenges, and ease of implementation of pharmacy dispensing) using chi-square and *t* tests where appropriate. We will also calculate the proportion of pharmacists who refused to dispense Mifeprex® during the study. In addition, feasibility will be assessed in qualitative analyses of open ended interviews with pharmacists about dispensing Mifeprex® in pharmacies.

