3.2 Pharmacist Arm

We will examine two primary outcomes and one secondary outcome related to the pharmacist dispensing model. Primary outcomes will include: 1) pharmacists who object to dispensing Mifeprex® and 2) pharmacists who report satisfaction with pharmacy dispensing of Mifeprex®, and the secondary outcome will be: 3) pharmacists' knowledge related to medication abortion.

Number of pharmacists who object to participate in dispensing Mifeprex® will be based on information reported by pharmacy managers and site research staff as well as pharmacists' who self-report objecting to dispensing Mifeprex® in their baseline survey. Pharmacy managers and site research staff will track pharmacists' participation in the training and Mifeprex® dispensing and report the number of pharmacists who refuse to dispense Mifeprex® to the coordinating study team. Using these data, we will calculate the proportion of pharmacists who refuse to dispense Mifeprex® during the study.

Number of pharmacists who report being satisfied with pharmacy dispensing of Mifeprex® will be based on survey data reported by pharmacists. At follow-up, we will assess satisfaction with pharmacy dispensing of Mifeprex® (ranging from very satisfied to very unsatisfied).

Difference in pharmacists' mean knowledge score related to medication abortion will be based on data collected in pharmacists' baseline and endline surveys. Knowledge scores will be based on a set of 15 items related to medication abortion for which respondents will select answers from multiple choice response options. Topics include medication abortion dosing regimen, biological processes during medication abortion, clinical outcomes, and federal and state policies relating to medication abortion. For pharmacists who complete at least 50% of the items, we will calculate their average number of correct responses among completed items. All questions or statements include an "I don't know" response option, which we will code as incorrect.

We will first assess the internal consistency reliability of the 15 knowledge items and consider a Cronbach's alpha coefficient above .70 to be acceptable to examine the items as a combined score.¹⁹ We will run descriptive summary statistics for baseline responses describing participant characteristics, as well as follow-up responses on satisfaction with the model. We will conduct a

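### The primary refusal proportion has no stated denominator, and the protocol's pharmacist analysis set is not reconciled with the SAP's count of refusals

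*Protocol*

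**What the plan says.** **The outcome.** Refusal is one of the two measures of feasibility, the primary outcome (Protocol 3.1; SAP 3.2). Protocol 16.3 says: "We will also calculate the proportion of pharmacists who refused to dispense Mifeprex® during the study". No denominator is given.

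**The analysis set.** Protocol 16.1 says: "All eligible pharmacists who complete at least one survey or interview will be included in the pharmacist analysis". SAP 3.2 contains no pharmacist analysis set of its own and does not withdraw this one.

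**Who is a participant.** Protocol 8.2 says: "All pharmacists at the study pharmacies will be eligible". The synopsis likewise includes everyone providing services at a study pharmacy. Protocol 6.1 is narrower and defines participants as "any pharmacist working at one of the study pharmacy sites during the study who is willing to participate in the study". Training and dispensing are optional, and for surveys and interviews 8.2 says a pharmacist can take part "but may decline to participate in any".

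**Where the refusal count comes from.** Under SAP 3.2, managers and site research staff track training and dispensing and "report the number of pharmacists who refuse to dispense Mifeprex® to the coordinating study team". Self-reported objection in the baseline survey is added, and the proportion is computed from these data.

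**Headcounts.** Protocol 11.2 has a monthly call to the supervising pharmacist "to assess the number of pharmacists working at the site" and to ask whether anyone has started or stopped dispensing. Protocol 6.1 also expects to know, per site, how many pharmacists were trained and how many work there.

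**The concern.** A pharmacist who objects to dispensing can also decline training, surveys and interviews. Under 16.1 as written that person is outside the pharmacist analysis, so inclusion can depend on the outcome being measured. The SAP's sources can bring the same person back into the numerator, but nothing says what that numerator is divided by. A proportion whose two parts may come from different groups of people is not well defined, and this one is half of the primary outcome. Two analysts following the documents in good faith could report clearly different figures from the same data.

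**Working it through.** The documents give no expected refusal rate, response rate or precision target for pharmacists. The figure of up to 50 in Protocol 16.6 is a staffing ceiling. There is therefore no planned value to reproduce, and the inputs below other than 50 are assumptions.

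**Notation.** N = pharmacists on staff (50); k = refusers; m = refusers who complete no survey or interview; w = willing pharmacists who complete none.

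**Three readings**
- A, all staff in both parts: k/N.
- B, 16.1 governs both parts: (k − m)/(N − m − w).
- C, SAP count of refusers over 16.1 completers: k/(N − m − w).

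**Example 1: k = 8, w = 4** (38 of 42 willing pharmacists respond)
- A: 8/50 = 16.0%.
- m = 5: B = 3/41 = 7.3%; C = 8/41 = 19.5%.
- m = 8: B = 0/38 = 0%; C = 8/38 = 21.1%.

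**Example 2: k = 5**, where A is 5/50 = 10.0% (exact 95% CI 3.3% to 21.8%)

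| m | w | B | C |
|---|---|---|---|
| 0 | 10 | 5/40 = 12.5% | 5/40 = 12.5% |
| 1 | 0 | 4/49 = 8.2% | 5/49 = 10.2% |
| 1 | 10 | 4/39 = 10.3% | 5/39 = 12.8% |
| 3 | 0 | 2/47 = 4.3% | 5/47 = 10.6% |
| 5 | 0 | 0/45 = 0% | 5/45 = 11.1% |
| 5 | 10 | 0/35 = 0% | 5/35 = 14.3% |

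**Direction.** B is below A when N(k − m) < k(N − m − w), which simplifies to m/k > w/(N − k). So 16.1 understates refusal only if refusers fail to respond more often than willing pharmacists do. With k = 5, m = 1, w = 10 the rates are 1/5 = 20% and 10/45 = 22.2%, and B is slightly above A. C is never below A, and exceeds it whenever anyone fails to respond.

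**Can A be computed from what is collected?** Largely, yes. Manager reports supply the numerator without needing a survey, and headcounts are taken monthly. Three things are not specified:
- a cumulative count, since Protocol 6.1 and 8.2 expect staff changes and a monthly headcount does not say how many different people worked there;
- how manager reports and baseline self-reports are combined, given that pharmacist consents carry no names and e-mail addresses are not linked to survey answers (Protocol 8.2);
- how to classify someone who never trained and never dispensed but stated no refusal. The monthly question about starting and stopping does not identify that person.

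**The case against.** The strongest reply is that the SAP already settles the matter. Protocol 16 says: "The SAP will contain any modifications to the analysis plan described below". SAP 3.2 is the later and more specific text, and its refusal count does not depend on survey response. With 8.2 making everyone eligible and headcounts collected, reading A is the natural one, and under it nothing is lost. The surveys also try to reach refusers: baseline and endline both ask about refusal and the reasons (Protocol 11.1, 11.3), and payment does not depend on dispensing (18.4). Finally, this is a descriptive pilot with no threshold or test attached to the proportion.

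Much of this stands. A reader might infer from 16.1 that objectors who decline everything necessarily leave the refusal proportion and that the result is biased toward feasibility. The documents do not support that. Managers and site staff can report such pharmacists, and the arithmetic shows overstatement as readily as understatement.

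What the reply does not do is supply a denominator. The SAP has none, does not say that 16.1 is set aside for this outcome, and gives no rule for merging its sources. Reading A is sensible, but it is an inference.

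**Conclusion.** The point holds as a conflict between Protocol 16.1 and SAP 3.2 and as an undefined denominator for a primary measure. Applied as written, 16.1 gives a wrong refusal proportion whenever non-response is unequal (reading B), or whenever there is any non-response and the SAP count is used on top (reading C). In the examples the reported figure runs from 0% to 21.1% where the staff-wide value is 16%, and from 0% to 14.3% where it is 10%. With about 50 pharmacists, the second spread is of the same order as the sampling uncertainty (3.3% to 21.8%). These sizes rest entirely on the assumed numbers of refusers and non-respondents. The direction of error is not fixed. The need for a definition does not depend on those assumptions.

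**What to change.** In Protocol 16.1 and SAP 3.2:

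1. Confine the rule requiring a completed survey or interview to outcomes measured that way: satisfaction, knowledge and perceptions.
2. Define the refusal proportion as pharmacists who refused to dispense, divided by all pharmacists who worked at a study pharmacy at any time between dispensing launch and study end. Take the denominator from a cumulative, anonymous count kept through the existing monthly contact and manager reports.
3. State that manager reports and baseline self-reports are reconciled by site so that nobody is counted twice. Each pharmacy already has its own survey link, so the site is known.
4. Report pharmacists who never trained and never dispensed, with no stated refusal, as a separate count. They need not be classed as refusers, since scheduling or turnover may explain them.

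The cost is a wording change in both documents and slightly more detail in a contact that already takes place. The resulting refusal figure may be less favourable.
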